8.2.3 Patient compliance

During each stage of the program participants are required to input data as part of the CBT tasks. Participants will be divided into the following three groups:

- a) *Fully compliant*: participants who input data into the program during all five stages
- b) *Partially compliant*: participants who input data but not during all five stages
- c) *Non-compliant*: participants who do not enter any data into the program

We plan to conduct simple descriptive analysis to better understand trends in patient interaction with HeadOn.

8.2.4 Temporal change in secondary outcome measures

A number of secondary outcome measures are examined at both recruitment and at the 5-week follow-up (Rivermead post-concussion questionnaire, PHQ9 questionnaire, Pittsburgh Sleep Quality Index). We plan a descriptive analysis of the temporal changes in the aggregate scores of these measures.

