3 STUDY DESIGN

The HeadOn feasibility study is a prospective feasibility study of patients presenting to the Edinburgh Royal Infirmary and St John's Hospital Emergency Departments (ED) (**Figure 1**). Patients will be identified from the ED. Potentially eligible patients will be contacted by a member of the Emergency Medicine Research Group Edinburgh (EMERGE) research team and their consent will be sought for participation. Those not recruited at presentation to the ED will be contacted by telephone, text or email within two weeks of their concussion date to seek their participation in the study, again by a member of the EMERGE research team. After consenting, the participant will be taken through the registration process for the HeadOn program. For patients who are contacted after discharge they will be taken through registration process over the telephone or if preferable will be able to return to the ED to go over the process.

At registration the participant will be invited to complete a series of patient reported measures including the Rivermead post-concussion questionnaire, Pittsburgh Sleep Quality Index, PHQ9 questionnaire and FAST alcohol questionnaire within the HeadOn program. Alongside this, a series of researcher-led anonymised data points will be collected in a separate specially designed database including demographics, date of concussion, neurological and imaging findings which will all be collected from the medical notes and imaging reports. The HeadOn program runs for five weeks following which the participant will be invited to complete the same set of outcome measures. Alongside this, all the participant will be contacted (via telephone, text or email) by a member of the research team at week 5 to complete a further five measurements: Glasgow Outcome Score Extended, mHealth App Usability questionnaire, time to return to work and a healthcare utility questionnaire. Interested participants will be invited back within two months of enrolling in the study for a more detailed qualitative interviews about HeadOn. The study will recruit for a period of 6-months or up to 100 participants.

[figure not shown]

Figure 1: Schematic of HeadOn study design

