4.2 INCLUSION CRITERIA

- Patients aged 16 years and older (no upper age limit)
- Presenting to the ED with a concussion
- Concussion defined as a traumatically induced alteration of mental status (either defined as loss of consciousness and/or amnesia)
- Patient is Glasgow Coma Scale score of 13-15 on initial presentation to the ED
- Patient needs to be able to start using HeadOn within 14 days of their head injury

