5.2 CONSENTING PARTICIPANTS

Potentially eligible patients within the ED will be screened by the EMERGE team and approached and verbal consent gained on whether they would be interested to participate by a suitably trained member of the research team. Following this, the patient will be provided with a participant information leaflet (paper or digital). Potential participants will be recruited to the study within the four hour management window in ED. If the patient requires more time to decide

they can express an interest to participate after discharge from ED up to 14 days from the date of their concussion. Those interested to take part in the study will be consented by a member of the research team using the RedCap e-consent function which will be linked through the HeadOn website (www.headon-health.com/research).

Patients that are discharged before they agree to participate in the study or are identified post-discharge can be enrolled in the study by a suitably trained member of the research team up to 14 days from the date of their concussion. Initially patients will be contacted to see if they are interested in receiving information about the study. Those that are will be directed to the HeadOn website or sent the material by their preferred means (email/post). If they are interested in participating, the patients will be directed to the HeadOn website to be consented using the RedCap e-consent function.

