6. DATA COLLECTION

Data will be collected at four points during the study period: at baseline, during the HeadOn program, at the final 5-week follow-up and during a voluntary qualitative interview. Two forms of data will be collected: patient-reported and researcher collected.

At baseline, participants will complete four patient questionnaires within the HeadOn program (Rivermead postconcussion, PHQ9, Pittsburgh Sleep Quality and the FAST alcohol screen). Researchers will also capture demographic, clinical and imaging findings data taken from participants notes and investigation finding reports. During the HeadOn program, participants will undergo a series of ecological momentary assessments (EMAs) aimed at capturing information about their symptoms, mood, thoughts about their concussion and behaviour (**Appendix**). This includes a symptom and mood diary which will be delivered daily. Alongside this, a series of other EMAs are delivered to the participant at different stages of the program (**Figure 2**): Stage 3 (Alcohol tracker), Stage 4 (Thought diary) and Stage 5 (Goal setting). HeadOn generates automated reminders (by email or notification) to help keep participants engaged. In the final 5-week follow-up of the study, both participant-reported and researcher collected outcome measures will be captured. Participants will complete the following questionnaires digitally through the HeadOn program: Rivermead postconcussion, PHQ9, Pittsburgh Sleep Quality and FAST alcohol screen. The participant will also be contacted by a trained member of the HeadOn research team to complete four questionnaires: the mHealth app usability questionnaire, healthcare utility, return to work questionnaire and the Glasgow Outcome Score Extended (GOSE). The participant will also be reminded to complete the week 5 patient-reported questionnaires if they had not already done so. If the participant has not completed these questionnaires by week 6, then they will be contacted again by a member of the research team to complete these questionnaires.

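### Section 8.2.4 describes PHQ9 and sleep index change without days since injury, so the pooled change depends partly on enrolment timing and does not by itself show the post-injury course

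*Combined protocol and SAP*

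**What the plan says.** Section 8.2.4 names three measures taken at recruitment and at the 5-week follow-up: Rivermead, PHQ9 and the Pittsburgh Sleep Quality Index. The whole of the planned analysis is: "We plan a descriptive analysis of the temporal changes in the aggregate scores of these measures".

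The timing comes from other sections:

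- **Baseline forms.** Section 3: "At registration the participant will be invited to complete a series of patient reported measures".
- **Earliest enrolment.** Section 5.2: "Potential participants will be recruited to the study within the four hour management window in ED". The same section allows enrolment after discharge, up to 14 days from the concussion.
- **Latest start.** Section 4.2: "Patient needs to be able to start using HeadOn within 14 days of their head injury".
- **Follow-up forms.** Section 3: "The HeadOn program runs for five weeks following which the participant will be invited to complete the same set of outcome measures". Section 6 adds a later reminder: "If the participant has not completed these questionnaires by week 6, then they will be contacted again".
- **Injury date.** Section 3 lists it among the researcher-collected items: "demographics, date of concussion, neurological and imaging findings which will all be collected from the medical notes and imaging reports". No analysis in section 8 names time since injury.

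Appendix II prints a two-week recall period for PHQ9. Appendix III asks about the past month. The symptom diary in Appendix VIII asks about the current day and includes sleep disturbance and low mood items. Section 6 says of it: "This includes a symptom and mood diary which will be delivered daily". The only planned analysis of diary scores is their relation to GOSE, in section 8.2.6.

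**The concern.** One of the secondary objectives in section 2.1.2 is to describe how sleep disturbance and mood develop over the study period. A change score serves that purpose only if its starting point means roughly the same thing for everyone.

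Here it does not. Someone who completes the forms in the ED is reporting on the weeks before the injury. Someone who completes PHQ9 on day 14 is reporting only on the weeks after it. Pooling the two gives a baseline that is part pre-injury status and part early post-injury status, in proportions set by how patients happened to be recruited. A reader of the pooled change could take it for the course after concussion when, for some participants, it compares week 5 with life before the injury.

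Rivermead is left out of this point because the appendix text prints no recall period for it.

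**Working it through.** The plan states no figure for this analysis, so there is none to reproduce. The check is how much of each recall window falls before the injury.

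**Inputs**

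- Recall window W: 14 days for PHQ9 (Appendix II). The sleep index asks about a month (Appendix III), taken here as 30 days with a range of 28 to 31, because the form does not define it.
- Days from injury to the baseline form, d: 0 (section 5.2) to 14 (sections 4.2 and 5.2). No completion deadline is given for the baseline forms. A form completed after day 14 would have a lower share.
- Follow-up form: 35 days or more after starting the program (section 3), later if it follows the week-6 reminder (section 6).

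**Baseline window.** Pre-injury share = max(0, W − d) / W.

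| d | PHQ9, W = 14 | Sleep index, W = 30 |
|---|---|---|
| 0 | 14/14 = 100% | 30/30 = 100% |
| 3 | 11/14 = 78.6% | 27/30 = 90.0% |
| 7 | 7/14 = 50.0% | 23/30 = 76.7% |
| 10 | 4/14 = 28.6% | 20/30 = 66.7% |
| 14 | 0/14 = 0% | 16/30 = 53.3% |

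For the sleep index at day 14, a 28-day month gives 14/28 = 50.0% and a 31-day month gives 17/31 = 54.8%.

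**Follow-up window.** It opens on day d + 35 − W after injury. The earliest case is d = 0. PHQ9 then opens on day 0 + 35 − 14 = 21, and the sleep index, even with W = 31, on day 0 + 35 − 31 = 4. Both windows are wholly post-injury for every permitted d.

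**Cohort average.** The documents give no distribution of enrolment days, so these mixes are assumptions:

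- Even spread over days 0 to 14: mean d = 7, so the mean share is 50% for PHQ9 and 76.7% for the sleep index.
- 80/10/10% at days 0/7/14: PHQ9 80 + 5 + 0 = 85%; sleep index 80 + 7.67 + 5.33 = 93%.
- 10/10/80% at days 0/7/14: PHQ9 10 + 5 + 0 = 15%; sleep index 10 + 7.67 + 42.67 = 60%.

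**What follows.** At d = 0 the baseline window holds no post-injury days, however respondents weight them. If they follow the printed recall period, the change for these participants compares week 5 with pre-injury status. For PHQ9 at d = 14 the baseline holds no pre-injury days. Between these ends, the mix of states in the baseline moves with d.

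**The case against.** **The analysis is only descriptive.** Section 8.2.4 makes no claim of recovery or efficacy, the study is a single-arm feasibility study, and nothing forbids a table by days since injury. This limits the consequences, and it is why the primary endpoints are untouched. It does not remove the point: description is what the objective asks for, and the pooled change as written does not deliver it.

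**The shares might be read as thresholds.** A reader might infer that a participant registering on day 7 must recover more than 50% of the post-injury rise in PHQ9 before any improvement shows, or that improving participants will appear to worsen. The documents do not support that. It would require each score to be a linear average of daily states, whereas the forms use frequency bands. Take a symptom absent before injury and present every day since. At day 7 it covers 7 of 14 days, which is not more than half, so the PHQ9 item scores 1; a linear average gives 0.5 × 3 = 1.5. At day 8 it scores 2; a linear average gives (8/14) × 3 = 1.71. How respondents weight days in recall is also unknown.

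**The sleep baseline might be called mainly pre-injury.** That label also goes too far. If weight falls linearly to zero at the start of the window (an assumption), the pre-injury share is ((30 − d)/30)²: (21/30)² = 49% at day 9 and (16/30)² = 28% at day 14. What survives is that the window includes pre-injury days at every permitted enrolment day.

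**Stratifying does not separate the groups.** This is correct. With strata of 0–3, 4–7 and 8–14 days, the PHQ9 shares are 79–100%, 50–71% and 0–43%, so each stratum contains mixed baselines. Showing change against the interval makes the mixture visible but does not remove it.

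**The diary is a different measure.** This is also correct. Diary items begin only after registration and depend on engagement, which is itself a primary outcome. They can supplement PHQ9 and the sleep index but not replace them.

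**Conclusion.** The point holds as a weakness in a secondary descriptive analysis and should be corrected. Following section 8.2.4 as written gives a pooled change whose starting point varies, by calendar days, from wholly pre-injury to wholly post-injury for PHQ9, and from wholly pre-injury to about half pre-injury (50–55%) for the sleep index. The end point is wholly post-injury for both. The result depends partly on recruitment timing and does not by itself describe the post-injury profile of sleep and mood.

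This rests on the printed recall periods, on baseline forms being completed between day 0 and day 14, and on a month of 28 to 31 days. The calendar arithmetic is firm. Its effect on scores is not quantified, and the documents do not allow it to be. The firm case is the day-0 form. It would be wrong to conclude that the planned analysis must show worsening in people who are improving, or that the compliance and usability results are in doubt.

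**What to change.** Amend section 8.2.4 as follows.

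1. Tabulate days from injury to baseline completion, and show PHQ9 and sleep index change against that interval, by plot or in broad strata. State that only day-0 baselines are wholly pre-injury, and that only PHQ9 baselines from day 14 are wholly post-injury.
2. State that the baseline sleep index includes pre-injury time at every permitted enrolment day (about half or more of the calendar window), and do not present its change as post-concussion recovery.
3. As a supplement to the declared endpoints, plot the diary's sleep disturbance and low mood items against days since injury, with the number of participants contributing on each day.

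**Data needed.** The date of concussion and the diary are already collected. The documents do not show that form completion dates are recorded: the data types listed for the HeadOn app in Table 2 do not include one. The team should confirm this and use the registration date if the form date is missing.

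**Cost.** No new questionnaire or visit is needed. Strata will be small: at most 100 participants, so about 100/3 = 33 in each of three if evenly spread, before missing forms. The headline figure becomes less simple, and the diary profile covers only engaged users on days after registration.

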8.2.5 Functional outcome

The Glasgow Outcome Scale extended is being used to determine functional outcome in this study. It is an 8-level scale with 8 representing a complete recovery down to 1 which is death. We plan on dichotomising participants to complete recovery (score 8) versus incomplete recovery (<8). Logistic regression will then be used to examine the predictive role of a range of admission data points (demographics, clinical findings (LOC vs no LOC, amnesia vs no amnesia) and admission patient reported measures (Rivermead, PHQ9).

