5. PARTICIPANT SELECTION AND ENROLMENT

5.1 IDENTIFYING PARTICIPANTS

Patients will be identified in the ED. The EMERGE team, where it is locally agreed that they are part of the clinical care team, will identify patients using triage information and clinical or electronic records in the ED at presentation or through screening of admission logs. In this case, it is anticipated they would identify patients and make the first approach. Any member of the clinical team who has received general and trial specific training and is on the delegation log may also identify patients in this way.

Patients with concussion do not typically have long stays in ED and can be discharged after a few hours. Those patients that are not approached at admission or not recruited at presentation to the ED will be identified through ED admission logs by a member of the EMERGE team and will be contacted within two weeks from the date of their concussion to seek their participation in the study by a suitably trained member of the research team.

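### Section 8.2.5 calls Rivermead and PHQ9 admission predictors, but they are registration scores from day 0 to 14 after injury, and GOSE follows at about day 35 to 49

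*Combined protocol and SAP*

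**What the plan says.** Section 8.2.5 splits GOSE into score 8 against anything lower. It plans a logistic regression on data described as coming from admission: demographics, loss of consciousness, amnesia and "admission patient reported measures (Rivermead, PHQ9".

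Other sections place those two forms at a different moment:

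- Section 3: "At registration the participant will be invited to complete a series of patient reported measures". Registration follows consent and, for people contacted after discharge, is done by telephone or on a return visit to the ED.
- Section 4.2: "Patient needs to be able to start using HeadOn within 14 days of their head injury".
- Section 5.2: patients who leave before agreeing or "are identified post-discharge can be enrolled in the study", "up to 14 days from the date of their concussion".
- Section 5.1 explains why this route exists: "Patients with concussion do not typically have long stays in ED and can be discharged after a few hours".
- Section 8.2.4 gives the same time point another name: "A number of secondary outcome measures are examined at both recruitment and at the 5-week follow-up".

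GOSE is collected by researcher contact at week 5 of the five-week programme (sections 3 and 6). Table 1 counts those weeks from allocation. Section 3 lists the date of concussion among the data collected, but section 8.2.5 names no covariate derived from it.

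**The concern.** A symptom score given two weeks after a concussion contains information that nobody in the ED had. If it enters the model as an admission variable, the published sentence will say that outcome was predicted at admission, and for late registrants that will not be true. Loss of consciousness, amnesia and demographics do not have this problem.

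The outcome has a related difficulty. Recovery is scored yes or no at a fixed interval from registration, so participants are classified at different times since injury. The recovery proportion then depends partly on how many people enrolled late. The study is meant to guide later controlled trials (section 1.2), so both results may be carried into their planning.

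**Working it through.** The plan gives no figure of its own on this point to reproduce. The target of 100 participants does not depend on it.

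**Inputs from the documents.** Delay from injury to registration, d: 0 to 14 days (4.2, 5.2). Registration to GOSE: 5 weeks = 35 days (3, 6, Table 1). **Not given:** the share registering after discharge, the recovery course, and a collection window for GOSE.

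**Step 1, calendar.** Form day = d, so 0 to 14. GOSE day = d + 35, so 0 + 35 = 35 to 14 + 35 = 49. The ratio is 49/35 = 1.4.

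**Step 2, recovery proportion (assumed course).** Let P(T) = 2^(−T/m) be the proportion not fully recovered at day T, with median recovery time m. Assume half register on day 0 and half evenly over days 1 to 14. The mix is then ½·P(35) + ½·mean of P(36) to P(49).

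| m (days) | P(35) | P(49) | Mean of P(36) to P(49) | Mix | P(35) − mix |
|---|---|---|---|---|---|
| 20 | 29.7% | 18.3% | 23.1% | 26.4% | 3.3 points |
| 35 | 50.0% | 37.9% | 43.2% | 46.6% | 3.4 points |
| 60 | 66.7% | 56.8% | 61.3% | 64.0% | 2.7 points |

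A second assumed model lets each person's symptom score decay exponentially, with median time constant 14, 20 or 30 days, and the same half-late mix. Incomplete recovery is about 20, 39 and 62% if all are seen at day 35, 8, 21 and 43% if all are seen at day 49, and 16, 33 and 57% in the mix. The mix differs from day 35 by 4, 6 and 5 points.

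**Step 3, discrimination (assumed).** The AUC of the form as collected is compared with that of an injury-day form for the same GOSE, with half registering late.

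- Individual decay model: 0.78, 0.77 and 0.78 against 0.72, 0.72 and 0.73, an excess of 0.05 to 0.06.
- Correlated-symptom model (week-to-week correlation 0.80 to 0.95, m of 20, 35 or 60 days): an excess of 0.01 to 0.02. With everyone late it is 0.02 to 0.03; with everyone registered in the ED it is 0.

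**Step 4, what one delay term does.** In the middle case of the decay model, the odds ratio per 10 points is 2.01 without a delay term and 2.04 with it, while a true day-0 score gives 1.69. A delay main effect accounts for timing, but it does not turn a registration score into an admission score.

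**Step 5, why only one term.** If contact is on schedule, days to GOSE = days to form + 35 exactly, so the two cannot both be estimated. With contact lateness assumed half-normal (scale 2 days), they still correlate at 0.97.

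**The case against.** The strongest defence is that anchoring GOSE to the end of the programme is deliberate. It fits the secondary objective of describing function once HeadOn is finished, and it holds the form-to-outcome interval at five weeks. Other sections call the time point registration, baseline or recruitment, so admission may be loose wording, and the plan does not claim to build an ED prediction tool. The regression is also secondary, in a feasibility study whose primary endpoints are compliance and usability. All of this stands and limits the weight of the point. It does not repair section 8.2.5, which as written would report an admission prediction.

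A reader might infer that the plan is shown to overstate predictive accuracy. The documents do not support that. Every input to the illustrations beyond the calendar is assumed, and the two models disagree on size. At 100 participants the sampling SD of the AUC is 0.05 to 0.06 under the decay model, as large as the biggest excess found. Pooling could even weaken an association: PHQ9 asks about the last two weeks (Appendix II), which is mostly pre-injury on day 0 and wholly post-injury on day 14.

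A reader might also take "If the participant has not completed these questionnaires by week 6" to show that GOSE can drift without limit. In section 6 that sentence follows the reminder about the week-5 patient-reported forms, whereas GOSE is collected by the researcher. It is fair to say that no GOSE window is stated, but this sentence is not evidence of an open one.

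**Conclusion.** The point holds as a matter of labelling and timing. Rivermead and PHQ9 are registration measures taken on day 0 to 14. GOSE is taken at about day 35 to 49. The planned model accounts for neither spread. This follows from the documents alone and needs no assumption beyond contact at the scheduled week 5.

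The numerical consequence is not established. If half register late, the assumed courses shift the pooled incomplete-recovery proportion by about 3 to 6 points and raise the AUC credited to the form by 0.01 to 0.06. Both effects vanish if everyone registers in the ED. The gaps between day 35 and day 49 are larger, but they compare groups seen entirely at one extreme or the other, so they should not be read as the error in the reported figure. The direction of any bias in the odds ratio is open. The weight is moderate: the correction is worth making because it is cheap and prevents a wrong conclusion.

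**What to change.** In section 8.2.5:

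1. Call Rivermead and PHQ9 registration measures and word the conclusion as prediction from registration. Keep admission for demographics, loss of consciousness and amnesia.
2. Add one term, days from injury to registration, computed from the date of concussion. It also carries the GOSE timing, so do not add days to GOSE as a second term.
3. Repeat the model in participants registered during their initial ED attendance (day 0), excluding those who return to the ED later to register. Base any statement about admission prediction on this subset. Prefer it to score-by-time interactions: with two scores these add two more terms, and at 100 participants a simplified model with a single score had only 14 to 20% power to detect one under the decay model.
4. Report the injury-to-form and injury-to-GOSE intervals, and show the proportion with complete recovery by time since injury.

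A rule setting late week-5 forms to missing is not needed for this point and would discard data.

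**Cost.** Wording, one covariate and one repeat analysis, all from data already planned. The subset is smaller. If half of 100 participants register in the ED (assumed), standard errors grow by roughly √(100/50) = 1.41; if a quarter do, by √(100/25) = 2.
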